8.1 Screening

Screening will consist of two visits and will be flexible in duration (4-10 weeks), based on the time required to washout prior anti-rheumatic medications, during which time the subject will sign the ICF, be evaluated for eligibility and have sufficient time for potential medication washout, in addition to all other assessments indicated in [Table 8-1](#).

During the first screening visit, initial assessments will be performed as outlined in [Table 8-1](#). At that visit the duration of the washout period will be determined. The second screening visit will be performed as follows:

- If the washout period is \leq 4 weeks the investigator should proceed directly to visit 2 on the same day and complete all assessments
- If the washout period is more than 4 weeks, the subject will be instructed to initiate necessary washout regimen, and return for Visit 2 within 4 weeks of the target randomization date (i.e., in all cases, Visit 2 should not happen earlier than 4 weeks prior to randomization).

If subjects do not have a chest X-ray or MRI available within 3 months of screening, the X-ray should be performed after it is certain the subject meets inclusion/exclusion criteria in order to minimize unnecessary exposure to radiation.

All subjects evaluated at Visit 1 and 2 for Inclusion/Exclusion criteria should not be screen failed on the basis of a medication requiring washout, unless the subject will be unable to complete the washout in the appropriate time frame before randomization.

8.1.1 Information to be collected on screening failures

Subjects who discontinue from the study prior to randomization are considered screening failures.

If a subject discontinues before entering the double-blind treatment period at BSL, IRT must be notified within 2 days and the reason for not being randomized will be entered on the appropriate eCRF page. In addition, only the following eCRFs should be completed: Demography eCRF, Informed Consent eCRF, Inclusion/Exclusion eCRF, and the Adverse event (AE) eCRF should be completed for any Serious Adverse Events (SAEs) that occurred during the screening period.

Adverse events that are not serious will be followed by the investigator and collected only in the source data.

All subjects who have signed informed consent and are randomized into the double-blind treatment period at BSL will have all adverse events **occurring after informed consent is signed** recorded on the Adverse Event CRF.

Investigators will have the discretion to record abnormal test findings on the medical history CRF whenever in their judgment, the root cause for the test abnormality occurred prior to the informed consent signature.

8.2 Subject demographics/other baseline characteristics

Subject demographic and baseline characteristic data to be collected on all subjects and recorded in the eCRF include:

- Age, sex, race, ethnicity and source of subject referral
- Relevant PsA/Psoriasis and general medical history/current medical condition data until the start of study treatment, such as date of diagnosis of PsA/Psoriasis, previous PsA/Psoriasis therapies with the status of prior TNF α inhibitor use, cardiovascular medical history, and smoking history

Whenever possible, diagnoses and not symptoms will be recorded.

8.3 Efficacy

The efficacy outcome measures used in this study are the standard measures used across all PsA trials and required for filing. All efficacy assessments should be performed prior to administration of study treatment.

- American College of Rheumatology (ACR) 20, 50 and 70 responses
- Swollen Joint Count (SJC)/Tender Joint Count (TJC)
- Patient's global assessment of disease activity (VAS)
- Physician's global assessment of disease activity (VAS)
- Patient's assessment of PsA pain intensity (VAS)
- Health Assessment Questionnaire – Disability Index (HAQ-DI $^{\circ}$)
- [REDACTED]
- High sensitivity C-Reactive Protein (hsCRP)
- Erythrocyte Sedimentation Rate (ESR)
- [REDACTED]
- Psoriatic Arthritis Disease Activity Score (PASDAS)
- Patient's global assessment of psoriasis and arthritis disease activity (VAS)
- Minimal disease activity
- Leeds Dactylitis Index (LDI) and dactylitis count
- Leeds Enthesitis Index (LEI)
- [REDACTED]
- Psoriasis Area and Severity Index (PASI)
- [REDACTED]
- Modified Nail Psoriasis Severity Index (mNAPSI)
- Physician global fingernail disease severity assessment (VAS)
- [REDACTED]

Patient reported outcomes (PROs) will be collected using the ediary technology.

The subject should must be given the PRO measure(s) to be completed at the scheduled visit before any clinical assessments are conducted

Details relating to the administration of all PROs are provided in [Appendix 16.12](#).

8.3.1 American College of Rheumatology (ACR) response

The ACR response ([Appendix 16.4](#)) will be used to determine efficacy ([Felson et al 1995](#)). A subject is defined as an ACR 50 responder if, and only if, the following three conditions hold:

- ≥ 50% improvement in the number of tender joints (based on 78 joints)
- ≥ 50% improvement in the number of swollen joints (based on 76 joints)
- ≥ 50% improvement in three of the following five measures:
 - Patient's global assessment of disease activity (measured on a VAS scale, 0-100)
 - Physician's global assessment of disease activity (measured on a VAS scale, 0-100)
 - Patient's assessment of PsA pain (measured on a VAS scale, 0-100)
 - Health Assessment Questionnaire- Disability Index (HAQ-DI[®]) score
 - Acute phase reactant (hsCRP or ESR)

ACR20 = 20 % improvement in at least 3 of the 5 measures and 20 % improvement in the swollen and tender joint count.

ACR50 = 50 % improvement in at least 3 of the 5 measures and 50 % improvement in the swollen and tender joint count.

The ACR response is to be assessed at the visits shown in [Table 8-1](#)

8.3.2 Tender 78 joint count and swollen 76 joint count

Joint counts will be performed by the independent assessor(s) who must be well trained and part of the site personnel. Whenever possible, the same evaluator should perform these assessments at all visits (Refer to [Appendix 16.4](#) for more details).

During the open label phase of the study, as much as possible, the same evaluator should perform these assessments at all visits.

The 78 joints assessed for tenderness include the 2 temporomandibular, 2 sternoclavicular, 2 acromioclavicular joints, 2 shoulders, 2 elbows, 2 wrists, 2 first carpometacarpal, 10 metacarpophalangeal, 10 proximal interphalangeal, 8 distal interphalangeal joints of the hands, the 2 hip, 2 knee, 2 talo-tibial, 2 mid-tarsal, 10 metatarsophalangeal, 10 proximal interphalangeal, and 8 distal interphalangeal joints of the feet. All of these except for the hips are assessed for swelling. Joint tenderness and swelling are graded present (1) or absent (0). Synovial fluid and/or soft tissue swelling but not bony overgrowth, represents a positive result

for swollen joint count. Dactylitis of a digit in the foot or hand counts as one tender and swollen joint.

Data is recorded for all tender and swollen joints (right or left side), i.e. a box (no, yes or not applicable) needs to be ticked for all joints. The total number of tender and swollen joints (right and left) will be automatically calculated in the eCRF.

8.3.3 Patient's global assessment of disease activity

The patient's global assessment of disease activity will be performed using 100 mm VAS ranging from "very good" to "very poor", after the question, "*Considering all the ways psoriatic arthritis affects you, please indicate with a vertical mark (|) through the horizontal line how well you are doing today*".

8.3.4 Physician's global assessment of disease activity

The physician's global assessment of disease activity will be performed using 100 mm VAS ranging from no disease activity to maximal disease activity, after the question, "*Considering all the ways the disease affects your patient, draw a line on the scale for how well his or her condition is today*". To enhance objectivity, the physician must not be aware of the specific patient's global assessment of disease activity, when performing his own assessment on that subject.

[figure not shown]
8.3.5 Patient's assessment of PsA pain intensity

The patient's assessment of pain will be performed using 100 mm visual analog scale (VAS) ranging from "no pain" to "unbearable pain" after the question "*Please indicate with a vertical mark (|) through the horizontal line the most pain you had from your psoriatic arthritis today*".

8.3.6 Health Assessment Questionnaire - Disability Index (HAQ - DI)

The HAQ-DI[©] was developed by Stanford University and is one of the most widely used measures to assess the long-term influence of chronic disease on a subject's level of functional ability and activity restriction. The disability assessment component of the HAQ, the HAQ-DI, assesses a subject's level of functional ability and includes questions of fine movements of the upper extremity, locomotor activities of the lower extremity, and activities that involve both upper and lower extremities. There are 20 questions in eight categories of functioning including dressing, rising, eating, walking, hygiene, reach, grip, and usual activities. The stem of each item asks over the past week "Are you able to ..." perform a particular task. Each item is scored on a 4-point scale from 0 to 3, representing normal (normal, no difficulty [0]), some difficulty (1), much difficulty (2), and unable to do (3).

The purpose of the HAQ-DI in this study is to assess the functional ability of subjects with PsA. Refer to [Table 8-1](#) and [Appendix 16.9](#) for more details.

8.3.8 High Sensitivity C-reactive protein (hsCRP)

Blood for this assessment will be obtained in order to identify the presence of inflammation, to determine its severity, and to monitor response to treatment.

Since the results of this test may unblind study personnel, results from the central lab will be provided for screening and baseline only. The hsCRP results from samples collected during the treatment period will be revealed following database lock only.

8.3.9 Erythrocyte sedimentation rate (ESR)

Blood for ESR, which is helpful in diagnosing inflammatory diseases and is used to monitor disease activity and response to therapy, will be obtained at scheduled visits as indicated in Table 8-1.

8.3.11 Psoriatic Arthritis Disease Activity Score (PASDAS)

PASDAS is a new composite measure developed to access disease activity in Psoriasis (GRACE Project) (Helliwell et al, 2012). It is calculated by utilizing seven measures; the seven components are: Patient reported measures (excluding mental component summary score (MCS) of the medical outcomes survey Short Form-36 (SF-36-PCS)), skin, peripheral joint counts (tender and swollen joint counts), dactylitis (LDI), enthesitis (LEI), acute phase response (CRP) and patient & physician global VAS scores.

$$\begin{aligned} \text{PASDAS} = & (0.18 \times \sqrt{\text{Physician global VAS}}) \\ & + (0.159 \times \sqrt{\text{Patient global VAS}}) \\ & - (0.253 \times \sqrt{\text{SF36-PCS}}) \\ & + (0.101 \times \text{LN}(\text{Swollen joint count} + 1)) \\ & + (0.048 \times \text{LN}(\text{Tender joint count} + 1)) \\ & + (0.23 \times \text{LN}(\text{Leeds Enthesitis Count} + 1)) \\ & + (0.377 \times \text{LN}(\text{Dactylitis count} + 1)) \\ & + (0.102 \times \text{LN}(\text{CRP} + 1)) + 2 \times 1.5. \end{aligned}$$

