8.3.14 Leeds Dactylitis Index (LDI)

The Leeds Dactylitis Index (LDI) (Helliwell et al 2005) basic measures the ratio of the circumference of the affected digit to the circumference of the digit on the opposite hand or foot, using a minimum difference of 10% to define a dactylitic digit. The ratio of circumference is multiplied by a tenderness score, using a modification of LDI that is a binary score (1 for tender, 0 for non-tender). If both sides are considered involved, or the circumference of the contralateral digit cannot be obtained, the number will be compared to data provided in the standard reference tables (see Appendix 16.8 and Table 8-1). This modification is referred to as LDI basic and will be applied in this study. The LDI requires a finger circumference gauge or a dactylometer to measure digital circumference.

Dactylitis count

The dactylitis count is the number of fingers and toes with dactylitis, with a range of 0-20.

Presence of dactylitis

If dactylitis is present with any finger or toe, the subject is counted as a subject with dactylitis.

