## 1 Introduction

Data will be analyzed by Novartis according to the data analysis section 12 of the clinical study protocol. The statistical methodology is described below and any deviations from the protocol are documented. Additional detailed information regarding the analysis methodology is contained in the Appendix section.

This version of SAP covers the statistical and analytical plans of the CAIN457P12302 trial regarding the final DBL. As this is the Final DBL, analysis will only be done for long-term efficacy and safety. Analyses pertaining to Week 16 will not be repeated. Tables and listing for demographics, baseline disease characteristic, prior medication and medical history will not be reproduced. Any analyses related to the testing hierarchy will not be reproduced.

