### Psoriatic Arthritis Disease Activity Score (PASDAS)

PASDAS is a new composite measure developed to access disease activity in Psoriasis (GRACE Project) ([Helliwell 2012](#)). It is calculated by utilizing seven measures; the seven components are: Patient reported measures (excluding mental component summary score (MCS) of the medical outcomes survey Short Form-36 (SF-36-PCS)), skin, peripheral joint counts (Tender and Swollen joint counts), Dactylitis (LDI), Enthesitis (LEI), acute phase response (CRP) and Patient & Physician global VAS scores.

$$\begin{aligned} \text{PASDAS} = & (((0.18 \times \sqrt{\text{Physician global VAS}}) \\ & + (0.159 \times \sqrt{\text{Patient global VAS}}) \\ & - (0.253 \times \sqrt{\text{SF36-PCS}}) \\ & + (0.101 \times \ln(\text{Swollen joint count} + 1)) \\ & + (0.048 \times \ln(\text{Tender joint count} + 1)) \\ & + (0.23 \times \ln(\text{Leeds Enthesitis Count} + 1)) \\ & + (0.377 \times \ln(\text{Dactylitis count} + 1)) \\ & + (0.102 \times \ln(\text{CRP} + 1)) + 2) * 1.5. \end{aligned}$$

If any component measurement is missing, PASDAS will be missing. The patient global VAS defined in the PASDAS score is “VAS for PASDAS assessment” which measures patient’s global assessment of PSORIASIS and ARTHRITIS disease activity. The Physician global VAS is the Physician’s global assessment of PsA disease activity. Tender Dactylitis count is from “Leeds Dactylitis Instrument” CRF page with “Was dactylitis present?” = “Yes” and “Tender/non-tender” = “Tender”.

66-swollen / 68-tender joint counts for PASDAS assessment:

There are only 66 swollen and 68 tender joint counts which will be used for PASDAS assessment. That is the 10 joints in CRF: CMC1, DIP2 (FOOT), DIP3 (FOOT), DIP4 (FOOT), and (DIP5 (FOOT) both left and right, should not be counted in the swollen/tender joint count in PASDAS formula.

If the number of joints for which data were available (e.g., T) is less than 66/68 for the swollen/tender joint assessment, the number of swollen/tender joints (e.g., t) will be scaled up proportionately (i.e.,  $66*t/T$  or  $68*t/T$  for swollen or tender joint count).

[figure not shown]

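### Protocol 8.3.11 and SAP 2.5.1 print PASDAS formulas that differ in what the factor 1.5 multiplies, and the SAP is inconsistent about which dactylitic digits are counted

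*Protocol*

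**What the plan says.** **Formula.** Protocol 8.3.11 opens with the first weighted term, "PASDAS} = & (0.18 \times \sqrt{\text{Physician global VAS", and closes with "0.102 \times \text{LN}(\text{CRP} + 1)) + 2 \times 1.5". No bracket encloses the sum. SAP 2.5.1 has the same eight weights but opens "PASDAS} = & (((0.18 \times \sqrt{\text{Physician global VAS" and closes "0.102 \times \ln(\text{CRP} + 1)) + 2) * 1.5".

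**Dactylitis input.** Both formulas name a dactylitis count. Protocol 8.3.14 defines it without a tenderness condition: "The dactylitis count is the number of fingers and toes with dactylitis, with a range of 0-20". The SAP's own entry for the dactylitis count is likewise unrestricted. The SAP's note under the PASDAS formula then begins "Tender Dactylitis count is from" and restricts the source to digits recorded as both dactylitic and tender.

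**Joint input.** Protocol 8.3.2 describes 78 joints for tenderness and 76 for swelling. Section 8.3.11 does not say which joints enter PASDAS. The SAP does: "There are only 66 swollen and 68 tender joint counts which will be used for PASDAS assessment".

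**Role of the endpoint.** Change in PASDAS at Week 16 is H5 in the hierarchy of Protocol 12.5.1, analysed by MMRM. H6 to H11 are reached only if H5 is rejected. The supplied SAP covers the final database lock and says "Analyses pertaining to Week 16 will not be repeated".

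**The concern.** A multiplier that covers only the constant gives a different scale from one that covers the whole score. The constant comes to 3 either way, so the discrepancy is easy to miss in score levels. It appears in full in every change and between-arm difference, which are the quantities reported for H5.

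Of the two documents, only the protocol describes the Week 16 H5 analysis, while the SAP describes the scoring for the later lock. If each were followed as printed, Week 16 and Week 52 PASDAS results from one trial would be on different scales. A reader setting the Week 16 estimate beside the long-term results would be misled by a factor of 1.5.

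The dactylitis question is of another kind. Counting all dactylitic digits or only tender ones changes individual scores unevenly, so it is not a rescaling.

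**Working it through.** **Planning figure first.** Protocol Table 12-3 and SAP Table 3-3 give mean changes of −0.91 (placebo), −2.02 (150 mg, SD 1.359) and −2.37 (300 mg, SD 1.361), with 190 per arm and 99% power.

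- 150 mg: difference 1.11; 1.11 / (1.359 × √(2/190)) = 7.96; power above 99.99%.
- 300 mg: difference 1.46; 1.46 / (1.361 × √(2/190)) = 10.5; power above 99.99%.

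The printed 99% is met.

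**Bracket.** Let S be the sum of the eight weighted terms.

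- Protocol as printed: S + 2 × 1.5 = S + 3.
- SAP: (S + 2) × 1.5 = 1.5S + 3.
- Ratio of any change or difference, same inputs: ΔS / 1.5ΔS = 2/3.

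**Illustrative patient (assumed values).** The order is physician VAS, patient VAS, PCS, swollen, tender, LEI, dactylitis, CRP.

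- Baseline 60, 60, 36, 10, 20, 2, 2, 10: S = 1.394 + 1.232 − 1.518 + 0.242 + 0.146 + 0.253 + 0.414 + 0.245 = 2.408.
- Follow-up 20, 25, 44, 3, 6, 1, 0, 4: S = 0.805 + 0.795 − 1.678 + 0.140 + 0.093 + 0.159 + 0 + 0.164 = 0.479 (from unrounded terms).

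| | Baseline | Follow-up | Change |
|---|---|---|---|
| Protocol as printed | 5.41 | 3.48 | −1.93 |
| SAP | 6.61 | 3.72 | −2.89 |

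The ratio of changes is 0.667. If the counts also differ (baseline swollen 9, tender 18, dactylitis 1; follow-up tender 5), the SAP change is −2.65 and the ratio 0.727. The two-thirds factor is therefore exact only when the inputs are the same.

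**Effect on H5.** Dividing the change by 1.5 divides its SD by 1.5, and the baseline covariate is altered only linearly. The test statistic is unchanged: 0.74 / (0.906 × √(2/190)) = 7.96, as before.

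**Effect on reported size,** assuming Table 12-3 is on the ×1.5 scale:

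- Mean changes: −0.91/1.5 = −0.61; −2.02/1.5 = −1.35; −2.37/1.5 = −1.58.
- Differences: 1.11/1.5 = 0.74; 1.46/1.5 = 0.97.

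**Dactylitis count, SAP scale.**

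- One non-tender digit, count 0 or 1: 1.5 × 0.377 × ln 2 = 0.39.
- Count 1 or 2: 1.5 × 0.377 × ln(3/2) = 0.23.

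**Joint set, SAP scale.** Ten joints are dropped (78 − 10 = 68; 76 − 10 = 66). As an illustration, swollen 10 to 9 and tender 20 to 18 moves the score by 1.5 × [0.101 × ln(11/10) + 0.048 × ln(21/19)] = 0.02.

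**Bracket count.** The protocol line balances. The SAP line has one more opening than closing bracket, but the reach of its ×1.5 is still clear.

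**The case against.** The strongest reply is that nothing shows anyone programmed the protocol line literally. SAP 2.5.1 is the only operational derivation supplied. It has the outer bracket, the missing-component rule, the VAS sources and the joint scaling, and it is written as a general description of the variable. The Week 16 analysis had already been done and is not in these documents. This stands: the documents show two printed formulas, not a wrong result.

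The formulas were also read from PDF, and the SAP's own brackets do not balance. That justifies checking the original. It does not dispose of the point, because an artefact would have had to remove a bracket at each end of the protocol formula and leave it balanced.

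On joints, the protocol never says that PASDAS uses 78/76. A reader might infer a contradiction, but choosing a subset of collected joints is ordinary SAP detail. The protocol is silent, and the illustrated effect is about 0.02 points.

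On dactylitis, the protocol lists the component with a reference to the LDI, whose basic form multiplies by a tenderness score of 0 or 1, so it is not plainly opposed to a tender count. The clearer conflict is inside the SAP, between its formula and count definition on one side and its source note on the other.

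**Conclusion.** The two formulas differ as printed, and the difference concerns the scoring of an endpoint in the alpha-controlled hierarchy. If the protocol line were followed literally, changes, differences and confidence intervals would be two-thirds of the SAP-scale values for identical inputs, and Week 16 would not be on the scale of the long-term results. The 0.74 and 0.97 figures depend on the unstated assumption that Table 12-3 is on the ×1.5 scale.

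Two stronger readings are tempting and not supported. One is that the Week 16 PASDAS results are wrong by a factor of 1.5; that derivation is not visible, so no reported value is shown to be wrong. The other is that the H5 test is compromised. The bracket leaves its p-value and power unchanged. The choice of dactylitis count could alter the test because it is not a rescaling, but no calculation here shows that it would reverse the result, and planned power exceeds 99.99%.

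The SAP's dactylitis count does need settling, at 0.39 or 0.23 points for one non-tender digit at low counts. The joint set is a minor clarification.

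**What to change.** 1. Check the protocol's original PDF for a lost bracket. If the text is as read here, correct 8.3.11 to the SAP's bracketing: [sum of the eight terms + 2] × 1.5.
2. Close the unbalanced bracket in SAP 2.5.1.
3. Name one dactylitis count, all digits or tender digits only, in both formulas and make the SAP's source note agree with it.
4. Cross-reference the 68/66 joint set in 8.3.11.
5. Confirm and record which formula and counts the Week 16 H5 analysis used. If they match the reconciled definition, nothing more is needed. If only the bracketing differed, re-derive the Week 16 estimates and confidence interval. If the dactylitis count differed, rerun the test as well. Week 16 and Week 52 should end up on one scale.

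The cost is a wording correction in each document and one derivation check, with a rerun only if there is a mismatch. No new data are needed.

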8.3.11.1 VAS for PASDAS (Psoriatic Arthritis Disease Activity Score) assessment

Please indicate with a vertical mark (|) through the horizontal line your answer to the following question relating to the past week.

In all the ways in which your PSORIASIS and ARTHRITIS, as a whole, affects you, how would you rate the way you feel over the past week?

8.3.13 Minimal disease activity

The proportion of subjects achieving minimal disease activity (MDA) (Coates et al 2010) is assessed as 5 of the 7 following: ≤ 1 tender joint count, ≤ 1 swollen joint count, PASI ≤ 1 or BSA $\leq 3\%$, patient pain VAS ≤ 15 , patient global assessment of disease activity VAS ≤ 20 , HAQ-DI[®] ≤ 0.5 , tender enthesal points ≤ 1).

